At least two days will elapse between IV infusions (Visits 2-5).

Two follow-up visits (Visits 6 and 7) will occur at days 15 (+/-5 days) and days 29 (+/- 7 days).

At least two days will elapse between Visits 5 and 6.

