8.1.3 Placebo run-in

All participants will receive placebo at Visit 2, known as a placebo run-in. In addition, at Visit 3 pre-randomisation, participants must ensure they continue to fulfil placebo run-in inclusion criteria.

Figure 1: CONSORT Trial Flow Diagram: A Randomised Double-Blind Placebo-Controlled Trial of Scopolamine in Bipolar Disorder

Note timeline between visits:

Visit 1 and 2: ≤14 days. Can also occur on the same day and thus data from screening visit does not need to be replicated at Visit 2.

Visit 2 and 3: ≥2 days and ≤7 days

Visit 3 and Visit 4 and Visit 5 and Visit 6: ≥2 days

Visit 6 and Visit 7: ≥3 days

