Procedures	Visit 1 Screening	Visit 2			Visit 3			Visit 4			Visit 5			Visit 6 Day 15 (± 5 Days) Follow-Up	Visit 7 Day 29 (± 7 Days) Follow-Up		
		PLACEBO			Randomisation Day 0 Scopolamine or Placebo			Day 4 (± 2 Days) Scopolamine or Placebo			Day 8 (± 2 Days) Scopolamine or Placebo						
		IV Infusion	IV Infusion	IV Infusion	Pre	During	Post	Pre	During	Post	Pre	During	Post				
Infusion administration		X				X			X			X					
Adverse Events		X	X	X	X	X	X	X	X	X	X	X	X	X	X		
Cannulation Site Check		X		X	X		X	X		X	X		X				
POMS (Optional)		X		X	X		X	X		X	X		X		X		
CANTAB ** (Optional)			X			X								X			
WAIS * (Optional)			X*			X*			X*			X*	X*	X*	X*		
NEO-PI-FFI * (Optional)			X*			X*			X*			X*	X*	X*	X*		
PRISE (Optional)			X			X			X			X					
Subjective Assessment															X		

Randomisation will only occur at Visit 3 after HDRS is demonstrated to be ≥ 8 and YMRS < 6 . These measures will be conducted pre-randomisation (and consequently also pre-infusion).

Pre-infusion vital signs should be taken post cannulation. Post-infusion vital signs within 15 minutes of infusion stopping and 50 to 90 minutes post-infusion.

Visit 6 and 7 can be conducted by telephone in limited circumstances if a participant has withdrawn or is unwilling/unable to attend clinic at the scheduled time.

* Can be undertaken at any of the marked visit

** These include Paired Associates Learning (PAL), Spatial recognition, Delayed Match to Sample, ID-ED Shift, motor screening and Eyes of the Mind tests.

***Only inclusion criterion 7 and exclusion criteria 21 and 22 are required to be met for randomisation at Visit 3 only

Δ Pregnancy test (serum pregnancy test and pregnancy urine dipstick), when required, for female participants only. Serum result confirmed prior to Visit 3.

◦ Blood tests for U&Es (Urine and Electrolytes), LFTs (Liver Function Tests) and TFTs (Thyroid Function Tests) should be confirmed within acceptable ranges in the previous 4 months of the Screening (Visit 1). Can be performed if required at Visit 1 or 2 (results must be confirmed as acceptable prior to infusion).

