#### ***5.2.2 Secondary endpoints***

1. Remission of depressive episode after the last IV treatment (measured objectively at Visit 6), and is defined as occurring when an individual has:
  - (i) a HDRS score <= 7
  - (ii) a Montgomery and Asberg Depression Scale (MADRS) score <6
2. Remission of depressive episode at follow-up (measured objectively at Visit 7)
  - (i) a HDRS score <=7
  - (ii) a MADRS score <6

SCOPE-BD NUIG-2017-002, Statistical Analysis Plan Version 1, 19/03/2024

3. Response to a depressive episode after the last IV treatment (measured at Visit 6) is defined as:

(i) a 50% reduction in MADRS score at Visit 6 compared to Visit 3

4. Response to a depressive episode at follow-up (measured objectively at Visit 7)

(i) a 50% reduction in MADRS score at Visit 6 compared to Visit 3

5. Improvement in mood symptoms measured with the HDRS and MADRS at visits 5, 6 and 7 compared to Visit 3.

6. Improvement in objectively measured overall functioning, measured with the Global Assessment of Functioning (GAF) at Visit 5, 6 and at follow-up at Visit 7 compared to Visit 3

7. Improvement in objectively rated illness severity, measured with the CGI-S at visits 4, 5, 6 and 7 compared to Visit 3 and CGI-I at visits 4, 5, 6 and 7 compared to Visit 3.

8. Changing subjective measured depressive symptoms with the Profile of Mood States (POMS) and Visual Analogue Scale (VAS).

(i) a reduction in POMS score post-infusion compared to pre-infusion at visits 2, 3, 4 and 5 across the six different factors of the POMS (tension, depression, anger, fatigue, vigour and confusion).

(ii) a reduction in VAS scores post-infusion compared to pre-infusion at visits 2, 3, 4 and 5 across 8 items (happy, restless, sad, anxious, anger, drowsiness and alertness).

9. A change in subjectively measured depressive symptoms at Visit 6 compared to Visit 3 as measured with the POMS and VAS.

10. A reduction in subjectively measured depressive symptoms at follow-up (Visit 7) compared to Visit 3 as measured with the POMS and VAS.

11. Psychiatric inpatient admission of a participant due to depressive episodes between Visit 2 and Visit 7.

12. Antidepressants medication use or change by a participant due to depressive episodes over the duration of the study (Visit 2 to Visit 7):

(i) Introduction of a new antidepressant (yes / no)

(ii) Increase in dose of an existing antidepressant (yes / no)

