## 6 Study Methods

### 6.1 General Study design and Plan

This is a single-site, randomised, double-blind, placebo-controlled, parallel, phase IIb clinical trial. Participants will receive IV Scopolamine or placebo in addition to their current treatment regimen. At Visit 2, all participants will receive placebo run-in (100mls of Saline IV). Within 7 days of Visit 2, participants will be assessed against the placebo run-in criteria and if these criteria are met they will be randomised (visit 3) to receive either placebo or 4 µg/kg Scopolamine IV in 100mls of Saline over 15 minutes at Visit 3 (Day 0), Visit 4 (days 2-6) and Visit 5 (days 6-10).

A flow-chart and schedule of assessments are included for greater clarity.

SCOPE-BD NUIG-2017-002, Statistical Analysis Plan Version 1, 19/03/2024

Note timeline between visits:

Visit 1 and 2: ≤14 days. Can also occur on the same day and thus data from screening visit does not need to be replicated at Visit 2  
Visit 2 and 3: ≥2 days and ≤7 days  
Visit 3 and Visit 4 and Visit 5 and Visit 6: ≥2 days  
Visit 6 and Visit 7: ≥3 days

SCOPE-BD NUIG-2017-002, Statistical Analysis Plan Version 1, 19/03/2024

Procedures	Visit 1			Visit 2			Visit 3			Visit 4			Visit 5			Visit 6			Visit 6			Visit 7			
	Screening			PLACEBO IV Infusion			Randomisation Day 0 Scopolamine or Placebo IV Infusion			Day 4 ( $\pm$ 2 Days) Scopolamine or Placebo IV Infusion			Day 8 ( $\pm$ 2 Days) Scopolamine or Placebo IV Infusion			Day 15 ( $\pm$ 5 Days) Follow-Up			Day 29 ( $\pm$ 7 Days) Follow-Up						
	Pre	During	Post	Pre	During	Post	Pre	During	Post	Pre	During	Post	Pre	During	Post	Pre	During	Post	Pre	During	Post	Pre	During	Post	
Signed informed consent	X						X**																		
Inclusion/Exclusion	X	X					X																		
Demographics																									
IWRS							X																		
Demography	X																								
MEHI	X																								
Medical/Surgical History/History BPD	X																								
Current Medication	X			X			X																		
Vital Signs – HR, BP & RR	X	X	X	X	X	X	X	X	X	X	X	X	X	X	X	X	X	X	X	X	X	X	X		
SCID-RV	X																								
HDRS	X	X																							
YMRS	X	X					X																		
AUDIT	X																								
Pregnancy Discussion	X	X					X																		
Contraception Advice	X	X					X																		
Serum Pregnancy Test a	X																								
Pregnancy urine dipstick A	X	X					X																		

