## 6.3 Randomisation and Blinding

Participants will be randomly assigned to receive either scopolamine or placebo in a 1:1 ratio. Randomly permuted blocks of sizes 4 and 6 will be used to ensure similar numbers of participants in each arm of the trial.

Randomisation will be stratified by the HDRS score at trial entry (a score of  $<23$  indicating a mild-moderate depressive episode and a score  $\geq 23$  indicating a severe depressive episode) to ensure greater balance between arms in the final trial sample and increase the efficiency of our treatment effect estimates.

A validated randomisation system will be used at Visit 3, (after HDRS and YMRS are completed) to randomise patients to either arm. This centralised system will ensure allocation concealment; preventing blinded trial staff from knowing which treatment group will be allocated. Blocks of randomly varying length will also reduce the predictability of the allocation sequence.

This trial will be conducted in a double-blind fashion with placebo control identical to Scopolamine solution to avoid bias in the assessment of outcomes. Site Investigators, site personnel, participants, and outcome assessors will be blinded to treatment allocation.

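### Secondary endpoints 11 and 12 start counting at Visit 2, before randomisation, which modestly dilutes the treatment comparison, mainly for antidepressant changes

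*SAP*

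**What the plan says.** - **Counting window.** SAP 5.2.2 item 11 counts "Psychiatric inpatient admission of a participant due to depressive episodes between Visit 2 and Visit 7". Item 12 has two separate yes/no parts, a new antidepressant and a dose increase, each counted "over the duration of the study (Visit 2 to Visit 7"). Protocol 8.12.1.2 items 11 and 12 match. Protocol 7.3.2 items 10 and 11 refer only to the whole study period and name no starting visit.
- **Start of treatment.** SAP 6.1 gives every participant a saline infusion at Visit 2. SAP 6.3 states "A validated randomisation system will be used at Visit 3". The visit timeline in protocol 8.1.3 reads "Visit 2 and 3: ≥2 days and ≤7 days".
- **End of the window.** Protocol 8.1 places Visit 7 at day 29, plus or minus 7 days.
- **Recheck before randomisation.** The footnote to protocol Table 2 reads "Only inclusion criterion 7 and exclusion criteria 21 and 22 are required to be met for randomisation at Visit 3 only". Those criteria cover HDRS, YMRS and a serious event during infusion. Protocol 8.3.5 adds a review for excluded medication.
- **Baseline for other outcomes.** The primary endpoint and the HDRS, MADRS, GAF and CGI changes are all measured from Visit 3.

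**The concern.** A participant who starts a permitted antidepressant during the run-in, or is admitted voluntarily, can still be randomised and is then recorded as having the event whichever arm follows. SAP 13.2 has no rule that removes or adjusts for such events, and SAP 5.3 derives nothing beyond change scores.

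Adding the same pre-treatment risk to both arms pulls the risk ratio toward 1. SAP 13.2 bases interpretation of secondary outcomes on point estimates and confidence intervals, so the attenuated quantity is the one that will be reported. The dilution works in both directions: it would also blur an increase in admissions on scopolamine. The documents give no reason for opening the window at Visit 2.

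**Working it through.** **The plan's own figures.** The only sample-size statement (SAP 7) concerns the primary endpoint. It reproduces: a difference of 12 with SD 13 needs 22 per arm, with t-test power 84.9% against the stated 85%. It does not bear on this point. No event rate, effect size or power is given for endpoints 11 and 12.

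**Share of the window before randomisation.** Share = run-in days / (run-in days + days from Visit 3 to Visit 7).
- Visit 7 on day 29: 2/31 = 6.5% to 7/36 = 19.4%.
- Extremes of the Visit 7 window: 2/38 = 5.3% to 7/29 = 24.1%.

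**Dilution.** Assumptions, none from the documents: constant hazard; placebo risk p over 29 days of 20% or 30%; true post-randomisation risk ratio 0.50; Visit 7 on day 29. The 25 per arm is the plan's figure.

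- Run-in risk, the same in both arms: q = 1 − (1 − p)^(run-in days/29).
- Counted risk: q + (1 − q) × post-randomisation risk.
- Counted risk difference: (1 − q) × true difference, so the proportional shrinkage equals q.

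| p | Run-in days | q | Placebo counted | Scopolamine counted | Risk ratio | Risk difference (points) |
|---|---|---|---|---|---|---|
| 20% | 2 | 1.53% | 21.22% | 11.37% | 0.536 | 10.0 → 9.85 |
| 20% | 7 | 5.24% | 24.19% | 14.72% | 0.608 | 10.0 → 9.48 |
| 30% | 2 | 2.43% | 31.70% | 17.07% | 0.538 | 15.0 → 14.64 |
| 30% | 7 | 8.25% | 35.77% | 22.01% | 0.615 | 15.0 → 13.76 |

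Expected run-in events per arm are 25q: 0.4 (20%, 2 days) to 2.1 (30%, 7 days).

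**Signal-to-noise ratio, 30% risk and 7-day run-in.** z = difference / √[p₁(1 − p₁)/25 + p₂(1 − p₂)/25].
- From Visit 3: 0.15 / √(0.30×0.70/25 + 0.15×0.85/25) = 0.15/0.1162 = 1.29.
- From Visit 2: 0.1376 / √(0.3577×0.6423/25 + 0.2201×0.7799/25) = 0.1376/0.1267 = 1.09.

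**Same scenario, log risk ratio.** SE = √[(1 − p₁)/(25p₁) + (1 − p₂)/(25p₂)].
- From Visit 3: √(0.0933 + 0.2267) = 0.566; |ln 0.50|/0.566 = 0.693/0.566 = 1.22.
- From Visit 2: √(0.0718 + 0.1417) = 0.462; |ln 0.615|/0.462 = 0.486/0.462 = 1.05.

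On the log-ratio scale the standard error falls, because more events are counted. The estimate shrinks proportionally more, so the signal-to-noise ratio still drops.

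**The case against.** The case for leaving the window alone has several sound parts.

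- **No bias toward an arm.** Run-in events precede allocation, so randomisation balances them in expectation. A reader might infer that the early window could create a spurious benefit. The documents do not support that, beyond chance imbalance of one or two events with 25 per arm.
- **Nothing confirmatory is at stake.** SAP 10.5 makes secondary analyses exploratory, and the primary endpoint runs from Visit 3 to Visit 6. Both z values above are well below 1.96, so neither window could settle the question.
- **Intervals do not widen on the ratio scale.** A reader might infer that they do. The log-ratio standard error above goes the other way.
- **Admissions fit the constant-hazard model poorly.** To count, a participant must be admitted for depression after Visit 2 and still be randomised within 7 days. Protocol 8.11 lists involuntary detention, ECT and imminent self-harm risk among reasons to discontinue. Voluntary admission is not barred, but such cases should be rare.
- **A run-in event does not use up all information.** The two parts of endpoint 12 are separate, so a start during run-in leaves a later dose increase countable.
- **Related data appear elsewhere.** SAP 14.3 tabulates serious adverse events by visit and arm, and SAP 12.2 counts medications added during the treatment period.

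These points limit the size of the problem. They do not remove it: neither set of tables redefines endpoints 11 and 12, and no rule excludes run-in events from them.

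**Conclusion.** The window opens 2 to 7 days too early for a comparison of randomised treatments. The consequence is modest attenuation, mostly in endpoint 12. Under the stated assumptions a true risk ratio of 0.50 is counted as about 0.54 with a 2-day run-in and 0.61 to 0.62 with a 7-day run-in. The risk difference loses 1.5% to 8.2%, and expected z falls from 1.29 to 1.09 at 30% risk with a 7-day run-in.

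The direction follows from the documents whenever run-in events occur and treatment has an effect. The size rests on assumed event rates, a constant hazard and an assumed risk ratio. The 24% share of the window should not be read as typical, since it needs the longest run-in together with the earliest Visit 7.

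This is worth correcting because the change is cheap and discards no information about treatment. It does not threaten the trial's main conclusion.

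**What to change.** - In SAP 5.2.2, count endpoints 11 and 12 from randomisation at Visit 3 to Visit 7.
- Report Visit 2 to Visit 3 admissions and antidepressant changes by arm, as baseline characteristics.
- State that recorded medication-change and admission dates will split events at Visit 3. Protocol 8.4.6 records psychotropic changes at every visit. For endpoint 11, an admission meets the hospitalisation criterion in protocol 10.1.3, and the adverse event form (protocol 10.3.1) records date of onset. Confirm that the admission date itself is captured.
- Make the same change in protocol 8.12.1.2 items 11 and 12 and in 7.3.2 items 10 and 11.

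**Cost.** A small SAP revision, plus a protocol amendment that goes through the review described in protocol 15.1. Make it before unblinding, and record it as protocol 11.9 requires for departures from the original statistical plan. No new visits or assessments are needed, provided the admission date is on file.

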7.3.2 Secondary Endpoints

1. Remission of depressive episode measured with the HDRS at Visit 6 compared to Visit 3.
2. Response to a depressive episode measured with the HDRS at Visit 6 compared to Visit 3.
3. Reduction of depressive symptoms (MADRS) at Visit 6 compared to Visit 3.
4. Improvement in objectively measured overall functioning (GAF) at Visit 6 compared to Visit 3.
5. Reduction in depressive symptoms as measured using the POMS after all IV infusion visits compared to before IV infusions at the same visit (Visits 2, 3, 4, 5).
6. Response and remission data measured with the HDRS at Visit 7 compared to pre-randomisation HDRS scores at Visit 3.
7. Reduction in subjectively measured mood symptoms using the POMS at follow-up visits (Visits 6 and 7) compared to pre-randomisation.
8. Reduction in depressive symptoms, measured with the MADRS at Visit 7 compared to MADRS scores at Visit 3.
9. Improvement in global functioning, measured with the GAF at Visit 7 compared to pre-infusion GAF scores at Visit 3.
10. Psychiatric inpatient admissions due to depressive episodes over the duration of the study.
11. Antidepressant medication usage or change in antidepressant medication dose due to depressive episodes over the duration of the study.
12. Adverse events over the duration of the study.
13. Post infusion side effects at all 3 IV treatment visits: Bradycardia, Hypotension, Dizziness and Sedation (Visits 3, 4 and 5)
14. Occurrence of a hypo (manic) episode over the duration of the study.
15. Improvement in motor processing, visual and spatial memory at Visit 6 compared to initial scores measured at Visit 2 or Visit 3 as measured on CANTAB.

8. Trial Design

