8.2.3 Exclusion criteria

Participants who meet any one or more of the following exclusion criteria at Screening (Visit 1) or the Visit 2 will not be eligible to take part in the trial:

1. History of other Axis I diagnosis (including Recurrent Depressive Disorder or Psychotic Disorders such as schizo-affective disorder, conditions that can also present with depressive episodes)
2. History in the three months prior to Visit 2 of alcohol dependence syndrome or substance dependence syndrome.
3. Current use of oral steroid at Visit 1
4. A confirmed diagnosis of dementia
5. A diagnosis of intellectual disability (IQ < 70)
6. Participants with bipolar disorder that are euthymic in the investigators opinion at screening or Visit 2.

7. Participants with bipolar disorder that are hypomanic or manic (Young Mania Rating Scale (YMRS) > 6) at screening or Visit 2.
8. Presence of an established neurological disorder or other serious demyelinating conditions as determined by the treating physician (e.g. space occupying lesion, multiple sclerosis)
9. Current involuntary detention under the Mental Health Act (MHA) 2001 in an acute psychiatric inpatient unit
10. Severity of Bipolar Disorder is such that participation in a clinical trial is not appropriate because of the risk of imminent self-harm (based on clinical note review and review at screening visit by experienced clinician)
11. A history of an allergic reaction or sensitivity to Scopolamine (Hyoscine Hydrobromide). Participants will be asked at the screening visit about any previous treatment with scopolamine (Hyoscine Hydrobromide) to ascertain any previous allergic reaction or sensitivity to this agent.
12. A clinical diagnosis of narrow angle glaucoma, myasthenia gravis, paralytic ileus, pyloric stenosis, toxic megacolon and acute porphyria.
13. Individuals will be excluded from the study if currently prescribed anticholinergic medications, including Physostigmine, Biperiden and Procyclidine. Individuals will additionally be excluded if currently prescribed Tricyclic Antidepressants which are associated with significant anticholinergic properties (e.g. Amitriptyline and Nortriptyline) that are currently causing the participant to experience anticholinergic side effects (e.g. blurred vision, constipation, urinary retention, cognitive difficulties). No individuals will have anticholinergic medications stopped to allow them enter the trial.

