14. Bradycardia < 50 bpm, tachycardia > 100bpm or hypotension (systolic BP <90 and / or diastolic BP < 60) prior to IV administration of placebo or Scopolamine
15. A recent history in the last 6 months of symptomatic orthostatic hypotension or syncope.
16. Previous participation in this trial. Participation is defined as randomised. Participation in another trial within 3 months prior to Visit 1. Receipt of any investigational medicinal product (IMP) within 3 months prior to Visit 1.
17. Participants concurrently being administered Electroconvulsive Therapy (ECT).
18. Pregnancy, as determined by a positive urine dipstick at Visits 2, 3, 4, 5, positive blood serum result executed at Visit 2 and confirmed prior to infusion at Visit 3 or participants who are actively breastfeeding (female only).
19. Women of child-bearing potential are defined as all women physiologically capable of becoming pregnant, unless they are using highly effective methods of contraception during dosing of study treatment. Highly effective contraception methods include:
 - Female sterilization (have had surgical bilateral oophorectomy with or without hysterectomy) or tubal ligation at least six weeks before taking study treatment.
 - Male partner sterilization
 - Combination of any two of the following:
 - a. Barrier methods of contraception e.g. Condom
 - b. Use of oral, injected or implanted hormonal methods of contraception or other forms of hormonal contraception
 - c. Placement of an intrauterine device (IUD) or intrauterine system (IUS)
 - Women who are considered post-menopausal i.e. amenorrhea at least 12 months or undergone hysterectomy/bilateral oophorectomy
20. Any disorder, unwillingness or inability, not covered by any of the other exclusion criteria, which in the investigator's opinion, might jeopardise the participant's safety or compliance with the protocol

Placebo run-in exclusion criteria at Randomisation visit (Visit 3):

21. In addition to having completed Visit 2, participants must not be experiencing a hypomanic, or manic episode (YMRS >6).
22. A Serious Adverse Event (SAE) experienced during infusion which required medical intervention and whereby attending physician deemed it inappropriate for the participant to engage in future infusions.

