8.3.5 Treatment (Visit 3, Visit 4 and Visit 5)

At Visit 3, after assessment, participants will be randomised to placebo (n=25) (100mls IV Saline) or 4 µg/kg Scopolamine (n=25) IV in 100mls of Saline over 15 minutes and receive further infusions at Visits 4 (days 2-6) and 5 (days 6-10), with at least 2 days between IV infusions (see Table 2).

Assessments at Visits 3 prior to randomisation to ensure trial eligibility

- As per inclusion criterion 7 and exclusion criteria 21 and 22.
- HDRS ≥ 8 (indicating depressed mood of at least mild severity)
- YMRS <6 (indicating patient is not (hypo)manic)
- Medication review to ensure no participants have been prescribed medications which would exclude the participant from the trial between Visit 2 and Randomisation.
- Confirmation of pregnancy serum result (females only)

Randomisation via Interactive Web Response System (IWRS) (Visit 3 only)

Assessments at Visits 3, 4 and 5 are:

- Review of any medication changes
- Vital Signs recorded (BP, HR, RR) (pre-infusion but post cannulation)

- Dispensing via IWRS (Visit 3, 4, and 5)
- Completion of HDRS questionnaire (Visit 3 (completed as part of eligibility assessment), Visit 4, and 5, pre-infusion)
- Completion of MADRS questionnaire (Visits 3, 4 and 5, pre-infusion)
- Completion of YMRS (Visit 3 (completed as part of eligibility assessment), Visit 4, and 5, pre-infusion)
- Confirmation of pregnancy status (Urine dipstick) and contraception advice (Visit 3, 4 and 5, pre-infusion)
- Completion by participant of VAS (Visit 3, 4, and 5, pre-infusion)
- Completion by participant of the POMS (Visit 3, 4, and 5, pre-infusion) (optional)
- Completion of GAF questionnaire (Visits 3 and 5, pre-infusion)
- Completion of CGI-S (Visit 3, 4 and 5, pre-infusion)
- Completion of CGI-I (Visits 3, 4 and 5, pre-infusion)
- IV cannulation
- Cannulation site check (pre-infusion and post-infusion)
- Completion by participant of the POMS (minimum 15 minutes post-infusion (optional)
- Completion by participant of VAS (minimum 15 minutes post-infusion)
- Completion by participant of CANTAB subscales (Visit 3, post-infusion) (optional)
- Completion of WAIS (post infusion at Visit 3, 4, or 5) (optional)
- Completion of NEOPI-FFI (post infusion at Visit 3, 4, or 5) (optional)
- Vital Signs recorded (BP, HR, RR) (within 15 minutes of infusion stopping and 50 to 90 minutes post-infusion)
- Completion by participant of the PRISE questionnaire (post-infusion at Visit 3, 4 or 5 optional)

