10.2.1.3 Change in depressive or (hypo)manic symptoms

Change of baseline depressive symptoms or development of (hypo)manic symptoms based on clinical review are exempt from safety reporting unless they:

- (a) are associated with self-harm
- (b) are associated with uncharacteristic erratic behaviour
- (c) meet any one or more of the seriousness criteria

These events are collected on case report forms.

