13. Change in motor processing, visual and spatial memory (3 categorical variables) at Visit 6 compared to Visit 2 based on the Cambridge Neuropsychological Test Automated Battery (CANTAB) battery of tests.

SCOPE-BD NUIG-2017-002, Statistical Analysis Plan Version 1, 19/03/2024

14. Occurrence of a hypo (manic) episodes at visits 3, 4, 5, 6 or 7, as defined by a score of >6 on the Young Mania Rating Scale (YMRS).

15. Occurrence of other adverse effects as observed on monitoring of vital signs, reported by participants or measured utilising the Patient Rated Inventory of Side Effects (PRISE) questionnaire

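### The (hypo)mania endpoint counts only a YMRS above 6 on a visit day, and no planned analysis uses the non-reportable (hypo)manic symptoms that clinicians record on the CRF

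*SAP*

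**What the plan says.** Protocol 7.3.2 item 14 lists the endpoint as "Occurrence of a hypo (manic) episode over the duration of the study", with no rating scale and no restriction to visits. SAP 5.2.2 item 14 gives the rule that will be run, in which the scale is the Young Mania Rating Scale (YMRS): "Occurrence of a hypo (manic) episodes at visits 3, 4, 5, 6 or 7, as defined by a score of >6 on the". Protocol 8.12.1.2 item 14 has the same rule.

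Protocol 10.2.1.3 deals with events found clinically: "development of (hypo)manic symptoms based on clinical review are exempt from safety reporting unless they" are linked to self-harm, to out-of-character erratic behaviour, or to a seriousness criterion. It adds: "These events are collected on case report forms".

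SAP 5.3 says that endpoints draw on no further CRF variables apart from change scores. SAP 14.3.3 plans no adverse event analysis beyond those already listed.

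On entry limits, exclusion criterion 7 removes "Participants with bipolar disorder that are hypomanic or manic (Young Mania Rating Scale (YMRS) > 6) at screening or Visit 2". Criterion 21 says that at Visit 3 "participants must not be experiencing a hypomanic, or manic episode (YMRS >6"). Protocol 8.3.5 states the Visit 3 check differently: "YMRS <6 (indicating patient is not (hypo)manic"). The schedule footnotes in both documents also use the below-6 form.

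**The concern.** Switch into (hypo)mania is a natural safety question for a putative antidepressant in bipolar disorder, and safety is part of the primary objective. Protocol 6.1.2 notes that the earlier studies it describes included only 14 participants with bipolar disorder in a depressive episode, so this trial's own record of switches matters.

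Two features of the rule could distort that record. It uses one source, the visit-day score, although a second source is collected. And its threshold sits directly on top of the entry limit, with no requirement for a rise from baseline, a confirming rating or a clinical finding. The first can leave out events the trial already knows about. The second can let in small fluctuations.

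**Working it through.** The plan gives no rate, power or precision figure for this endpoint, so there is none to reproduce. Its only sample-size calculation concerns the HDRS. The check is a reading of the routes by which an event can be reported, followed by two illustrations.

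**1. Where can a (hypo)manic event appear?** Take a non-serious episode between visits, reviewed clinically, without self-harm or erratic behaviour, and with YMRS 6 or less at each visit.

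| Possible route | Counts it? | Source |
|---|---|---|
| (Hypo)mania endpoint | No, needs YMRS >6 at a visit | SAP 5.2.2 item 14 |
| Adverse event tables | No, exempt from reporting | Protocol 10.2.1.3; SAP 14.2 |
| YMRS variation as an adverse event | No, exempt | Protocol 10.2.1.5 |
| Inpatient admission | No, depressive episodes only | SAP 5.2.2 item 11 |
| Medication-change endpoint | No, antidepressants for depression only | SAP 5.2.2 item 12 |
| Additional adverse event analysis | None planned | SAP 14.3.3 |

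The event is on a CRF but in no planned switch or adverse event analysis.

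**2. How far apart are the ratings?** Windows: Visit 3 day 0; Visit 4 days 2–6; Visit 5 days 6–10; Visit 6 day 15 ± 5 = 10–20; Visit 7 day 29 ± 7 = 22–36. Longest gap = latest day of the later visit minus earliest day of the earlier one.

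| Interval | Nominal (days) | Longest (days) |
|---|---|---|
| Visit 3–4 | 4 | 6 − 0 = 6 |
| Visit 4–5 | 4 | 10 − 2 = 8 |
| Visit 5–6 | 7 | 20 − 6 = 14 |
| Visit 6–7 | 14 | 36 − 10 = 26 |

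**3. Illustration: what share of episodes overlaps a rating?** Assumptions: ratings on nominal days 4, 8, 15 and 29; the whole episode falls within days 1–29; onset is equally likely on each possible day; YMRS exceeds 6 only during the episode. An episode of L days has 30 − L possible onset days.

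| Length | No look-back | Rating also covers previous 6 days |
|---|---|---|
| 2 days | 7/28 = 25% | 22/28 = 79% |
| 4 days | 13/26 = 50% | 22/26 = 85% |
| 7 days | 16/23 = 70% | 22/23 = 96% |
| 10 days | 16/20 = 80% | 20/20 = 100% |

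The documents state no YMRS look-back period, so both columns are assumptions.

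**4. How small a change counts?** YMRS scores are taken as whole numbers. Under criterion 21 the highest score at randomisation is 6, and 7 meets the endpoint: 7 − 6 = 1 point. Under the below-6 text the highest is 5: 7 − 5 = 2 points.

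For illustration, assume independent rating error with SD 2. The chance of scoring 7 or more at one visit is P(Z > (6.5 − true score)/2), and over Visits 4–7 it is 1 − (1 − p)^4.
- True score 6: p = P(Z > 0.25) = 0.40, and 1 − 0.60^4 = 0.87.
- True score 4: p = P(Z > 1.25) = 0.106, and 1 − 0.894^4 = 0.36.

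The SD has no source in the documents. On the same assumption, a participant whose true score is 6 would pass three entry ratings with probability only 0.60^3 = 0.22, so the 0.87 describes an unusual participant.

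**5. Visit 3.** Its YMRS is taken before randomisation, and either entry text bars a score above 6. A correctly randomised participant cannot have a Visit 3 event.

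**The case against.** The plan has several fair points in its favour. YMRS >6 is the protocol's own marker of (hypo)mania in criteria 7 and 21, so using it for the endpoint is consistent, and protocol 8.12.1.2 can be read as making 7.3.2 operational. A prespecified blinded rating is more reproducible than clinical judgement. Cases with self-harm, erratic behaviour or seriousness do reach the adverse event tables. SAP 12.2 tabulates medications added during the treatment period, which may leave an indirect trace. Protocol 10.2.1.3 speaks of symptoms rather than episodes and names no specific CRF page or onset date. All of this stands. It argues for keeping the YMRS rule and adding to it, but it does not bring the recorded clinical events into any table.

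Four stronger readings are tempting and are not supported:

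- A reader might infer that a participant who misses Visit 7 is counted as having no episode. No section says so. SAP 9 analyses those with available follow-up data, and protocol 8.3.6 allows a telephone visit in limited circumstances.
- A reader might take the Visit 6–7 gap alone and conclude that only 15 to 50% of 4- to 7-day episodes are detected (4/26 = 15%, 7/14 = 50%). That isolates the longest interval and assumes no look-back. Over all four ratings the share is higher, as shown above.
- A reader might state flatly that a one-point rise suffices. That is exact only under criterion 21.
- A reader might expect a wrong formal conclusion on mood switch. SAP 10.5 treats secondary analyses as exploratory, and SAP 14 describes safety inference as underpowered and mainly descriptive.

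**Conclusion.** The point holds in this form. The rule to be run is narrower than the endpoint listed in protocol 7.3.2, and (hypo)manic symptoms recorded clinically but exempt from adverse event reporting are used in no planned analysis. The threshold is one or two points above the entry limit, depending on which conflicting text is applied, so a minor fluctuation can register as an episode.

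The size cannot be fixed from the documents. In an arm of 25, each event left out or wrongly included moves the reported proportion by 1/25 = 4 percentage points, so one or two could change the descriptive picture. The detection and false-positive rates are illustrations that depend on assumed episode length, look-back and rating error. That protocol 10.2.1.3 covers episodes arising between visits is a fair inference, not an explicit statement.

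This is a secondary, descriptive safety endpoint, and the primary HDRS analysis is unaffected. The change is worth making because it is cheap and bears on the trial's safety objective.

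**What to change.** Keep YMRS >6 as the prespecified component of SAP 5.2.2 item 14 and protocol 8.12.1.2 item 14, at the post-randomisation Visits 4 to 7. Removing Visit 3 is tidying and changes no result in correctly randomised participants.

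Add to SAP item 14 and SAP 14, by arm:
- a count and listing of (hypo)manic symptoms or episodes recorded on clinical review from the first randomised infusion to Visit 7;
- the combined count of participants with an event from either source;
- peak YMRS and change in YMRS from Visit 3, so that a crossing from just under the limit can be told from a substantial rise.

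The sponsor should reconcile criterion 21 with the below-6 wording in protocol 8.3.5 and the schedule footnotes in both documents.

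The cost is SAP and protocol wording and one extra table with its listing. YMRS scores are already collected at these visits, and protocol 10.2.1.3 says the clinical events are too. The downside is that the clinical component depends on judgement and on what the CRF captures. The sponsor should confirm that it records enough, for example an onset date, to place each event after the first randomised infusion.
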